6.6.17. Early Termination

Early termination from the study may occur due to loss to follow-up or withdrawal of consent by the subject. In accordance with legal requirements and ICH GCP, every subject or his/her legal representative has the right to withdraw from the study at any time and without providing reasons. If a subject is willing to provide a reason for withdrawal, this will be recorded in the CRF/source documents (see also 4.3.3 Individual Subject Stopping Rules; 5.2.6 Treatment Compliance).

7. ADVERSE EVENTS DOCUMENTATION

7.1. Definitions

An AE is defined as any untoward medical occurrence in a subject administered an investigational product and which does not necessarily have a causal relationship with the treatment. An AE can therefore be any unfavourable and unintended sign (including a clinically significant abnormal clinical laboratory finding, for example), symptom, or disease temporally associated with the use of an investigational product, whether or not related to the investigational product.

Sponsor Project Nº CL-5937-02

An adverse reaction (AR) is any AE for which there is a reasonable possibility the drug caused the AE. 'Reasonable possibility' means there is evidence to suggest a causal relationship between the drug and the AE Table 5. A suspected adverse reaction implies a lesser degree of certainty about causality than adverse reaction, which means any AE caused by a drug.

An AE may be:

- A new illness,
- Worsening of a concomitant illness,
- An effect of the study medication including comparator; it could be an abnormal clinical laboratory value as well as a significant shift from baseline within normal range which the investigator considers to be clinically important.

A serious adverse event (SAE) or reaction is any untoward medical occurrence that at any dose:

- Results in death.
- Is life-threatening,
- Requires inpatient hospitalization or prolongation of existing hospitalization,
- Results in persistent or significant disability or incapacity (defined as a substantial disruption of a person's ability to conduct normal life functions),
- Is a congenital anomaly or birth defect,
- Is an important medical event that may jeopardize the subject or may require intervention to prevent one of the other outcomes listed above (according to medical judgment of the investigator)

The following is not considered to be an SAE:

- Any elective procedures that require admission to hospital as well as any planned elective
 procedures (e.g., angioplasty) planned prior to signing a consent sent form are not considered
 SAEs (unless the underlying condition has worsened or the procedure results in a worsening of
 the subject's condition). This should be recorded in the medical history.
- A visit to an Emergency Room or other hospital department <24 hours that does not result in an admission to hospital (unless it is considered an important medical event or life threatening event) these should be recorded as an AE.

7.2. Severity Assessment

All AEs will be graded as mild, moderate, or severe according to the following definitions:

Mild: Causing no limitation of usual activities; the subject may experience transient slight

discomfort

Moderate: Causing some limitation of usual activities; the subject may experience annoying discomfort

Severe: Causing inability to carry out usual activities; the subject may experience intolerable

discomfort or pain

Every effort will be made to obtain an adequate evaluation of the severity.

Sponsor Project Nº CL-5937-02

7.3. Causality Assessment

The qualified investigator will determine the relationship of any AE to the study drug using the guidelines presented in Table 5

Table 5. Adverse Event Relationship to Study Drug

Relationship to Drug	Comment
Definite	A clinical event, including laboratory test abnormality, occurring in a plausible time relationship to drug administration and which cannot be explained by concurrent disease or other drugs or chemicals. The response to withdrawal of the drug (de-challenge) should be clinically plausible. The event must be definitive pharmacologically or phenomenologically using a satisfactory re-challenge (the drug is readministered to determine if the same reaction occurs) procedure if necessary.
Probable	A clinical event, including laboratory test abnormality, occurring in a plausible time relationship to drug administration and which cannot be explained by concurrent disease or other drugs or chemicals. The response to withdrawal of the drug (de-challenge) should be clinically plausible.
Possible	A clinical event, including laboratory test abnormality, with a reasonable time sequence to the drug administration, but which could also be explained by concurrent disease or other drugs or chemicals. Information on drug withdrawal may be lacking or unclear.
Unlikely ("Not related")	A clinical event, including laboratory test abnormality, with a temporal relationship to drug administration which makes a causal relationship improbable and in which other drugs, chemicals or underlying disease provide plausible explanations.
Not related	Any event that does not meet the above criteria; there is sufficient information that aetiology of the event is in no relation to the study drug.

7.4. Adverse Event Monitoring

For the purposes of this study, the monitoring period for AEs extends from the signature of informed consent (screening) until the follow-up visit.

From signature of informed consent (screening) to the first dose of the study, AEs will be recorded as screening events or as part of the medical history, as applicable.

AEs occurring after first dose of study medication will be indicated as treatment-emergent AEs (TEAEs) in the clinical study report.

Subjects will be questioned on their health status at each subject contact through to follow up visit. Openended questions will be asked.

During the study, all AEs spontaneously reported by the subject, observed by the clinical staff or elicited by general questioning will be recorded for all subjects and reported in the CRF/source documents.

Sponsor Project Nº CL-5937-02

If necessary, every effort will be made to obtain an adequate follow-up of the subjects. Should any subject choose to withdraw from the study, they will be advised of the safety precautions to be taken.

The Investigator must make every effort to follow-up any AE which remains unresolved as of the last visit regardless of attribution until judged resolved or a reasonable explanation for its persistence found or is deemed mild and safely resolving or the subject is lost to follow up.

In the case of AEs deemed related to the Investigational Product, every effort will be made to determine the final outcome.

Classification of AEs will be performed by System Organ Class (SOC) and Preferred Term (PT) using the most recent version of the Medical Dictionary for Regulatory Activities (MedDRA).

Concomitant medications will be coded using the most recent version of the World Health Organization drug dictionary.

7.5. Reporting of Pregnancy

Pregnancy in a female study subject shall be reported to the sponsor on the provided pregnancy reporting form within 24 hours of the knowledge of its occurrence by the qualified investigator or delegate (for pregnancies occurring during the course of the study or within 4 weeks after the last drug administration). Because of the possibility the foetus/embryo could have been exposed to the study drug through the parent and for the subject's safety, the pregnancy will be followed up to determine its outcome, including spontaneous or voluntary termination, details of birth, presence or absence of any birth defects, congenital anomalies, or maternal and/or newborn complications.

Pregnancy that occurs within 4 weeks after the last drug administration in a female partner of a male study subject shall be reported to the sponsor within 24 hours of the knowledge of its occurrence by the clinical site that such pregnancy occurred during the course of the study or right after. Because of the possibility that the foetus/embryo could have been exposed to the study drug through the parent and for the safety of the subject's female partner, the pregnancy will be followed up to determine its outcome, including spontaneous or voluntary termination, details of birth, presence or absence of any birth defects, congenital anomalies, or maternal and/or newborn complications and will be reported as an SAE.

The pregnancy will be recorded and reported by the clinical site to the sponsor. Pregnancy follow-up will also be properly recorded to ensure quality and completeness of the data belonging to the study drug and will include an assessment of the possible causal relation between the study drug and any pregnancy outcome. Any SAE experienced during pregnancy will be reported on an SAE Report Form.

Please see the Pregnancy Reporting Form Completion Guidelines for safety reporting instructions as per Diamond PV Safety Plan.

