	4. Have unexplained or refractory chronic cough for at least one year: a cough that is unresponsive to at least 8 weeks of targeted treatment for identified underlying triggers including reflux disease, asthma and post-nasal drip or unexplained cough; or a cough for which no objective evidence of an underlying trigger can be determined after investigation (see Appendix 1).						
	5. Awake Cough Count of ≥ 10 per hour (Cough Count at Screening).						
	6. A score of ≥ 40mm on the Cough Severity VAS at Screening.						
	7. Women of child-bearing potential must have a negative serum pregnancy test at Screening.						
	8. Women of child-bearing potential must use a highly effective contraception method from Screening through to the Follow-Up Visit. Acceptable birth						

control methods include:

- a. Intrauterine device (IUD) or intrauterine system (IUS);
- b. Tubal ligation; or male sterilization.
- c. When in line with the preferred life style of the subject, true and complete abstinence (not periodic abstinence) is acceptable.

For the purposes of this study, a female of childbearing potential is defined as any female who has experienced menarche and is pre-menopausal; a postmenopausal state is defined as no menses for 12 months without an alternative medical cause in a previously menstruating female.

9. Male subjects and their partners of child-bearing potential must use 2 methods of acceptable birth control (one method as listed in Inclusion Criteria 8), 1 of which must be a barrier method, and make no donation of sperm from Screening until 3 months after the last dose of study drug.

Exclusion Criteria:

Subjects are NOT eligible for this study if they meet any of the following criteria:

[figure not shown]
- 1. Current Smoker or Vaper.
- 2. Individuals who have given up smoking or vaping within the past 6 months, or those with >20 pack-year smoking history.
- Diagnosis of COPD, bronchiectasis, idiopathic pulmonary fibrosis based on clinician assessment.
- 4. Criteria No.4 removed from here in protocol v5.0. See Table 2 section 4.4 for details.
- 5. FEV1/FVC < 60%.
- 6. History of upper respiratory tract infection or recent significant change in pulmonary status within 4 weeks of the Baseline/Visit 2 (Day 0).
- 7. Criteria No.7 removed from here in protocol v5.0. See Table 2 section 4.4 for details.
- 8. Requiring concomitant therapy with prohibited medications or non-pharmacological therapy (see Table 2, Section 4.4).

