3. STUDY DESIGN

This is a Phase 2, multicentre, randomized, double-blind, placebo-controlled, two-period crossover, dose escalation study of BLU-5937 in subjects with unexplained or refractory chronic cough.

Subjects will be screened during a period of up to 14 days and undergo a screening 24-cough monitoring using an objective measure of coughs (VitaloJAK Vitalograph, Ltd.) to exclude the mild cougher subjects (< 10 cough/hr, from awake cough count).

Approximately 68 subjects who meet entry criteria will be randomized into the study. There will be two 16-day treatment periods (BLU-5937 or placebo) with a 10-14 days washout period between treatment periods. Each Period will consist of 4 escalating dose levels. Each dose level will be of 4 days duration.

The duration of treatment for each subject is as follows:

Screening Period: up to 14 days

Sponsor Project Nº CL-5937-02

- Baseline Period 1: 1 day
- Treatment Period 1 (BLU-5937 or Placebo):
 16 days (escalating doses of 25, 50, 100, 200 mg BID or placebo; 4 days for each dose)
- Washout: 10-14 days
- Baseline Period 2: 1 day
- Treatment Period 2 (Placebo or BLU-5937):
 16 days (escalating doses of 25, 50, 100, 200 mg BID or placebo; 4 days for each dose)
- Follow-Up Period: 10-14 days

Individual subject participation is expected to be approximately 74 days including Screening, Baseline, Treatment periods and Follow-Up period.

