4.1. Inclusion Criteria

[figure not shown]
Subjects who meet all of the following criteria will be included in the study:

- 1. Have provided written consent and are willing and able to comply with all aspects of the protocol.
- 2. Women and Men between 18 and 80 years of age inclusive.
- 3. Chest radiograph or CT thorax within the last 5 years from screening not demonstrating any abnormality considered to be significantly contributing to the chronic cough in the opinion of the Principal Investigator and Medical Monitor.
- 4. Have unexplained, refractory chronic cough for at least one year: a cough that is unresponsive to at least 8 weeks of targeted treatment for identified underlying triggers including reflux disease, asthma and post-nasal drip or unexplained cough; or a cough for which no objective evidence of an underlying trigger can be determined after investigation (see Appendix 1).
- 5. Awake Cough Count of ≥ 10 per hour (Cough Count at Screening).
- 6. A score of \geq 40mm on the Cough Severity VAS at Screening.
- 7. Women of child-bearing potential must have a negative serum pregnancy test at Screening.

Sponsor Project Nº CL-5937-02

- 8. Women of child-bearing potential must use a highly effective contraception method from Screening through the Follow-Up Visit. Acceptable birth control methods include:
 - a. intrauterine device (IUD) or intrauterine system (IUS);
 - b. tubal ligation; or male sterilization.
 - c. When in line with the preferred life style of the subject, true and complete abstinence (not periodic abstinence) is acceptable.

For the purposes of this study, a female of childbearing potential is defined as any female who has experienced menarche and is pre-menopausal; a postmenopausal state is defined as no menses for 12 months without an alternative medical cause in a previously menstruating female.

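### Section 7.5 covers partner pregnancies only to 4 weeks after the last dose, about 61–64 days short of the 3-month male precaution in synopsis criterion 9

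*Combined protocol and SAP*

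**What the plan says.** The partner paragraph of section 7.5 applies to "Pregnancy that occurs within 4 weeks after the last drug administration in a female partner of a male study subject". The site must tell the sponsor within 24 hours of learning of it. The same sentence ends by mentioning pregnancies during the study or *right after*, a term it does not define. The pregnancy is followed to its outcome, "and will be reported as an SAE", and the reason given is "Because of the possibility that the foetus/embryo could have been exposed to the study drug through the parent".

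Synopsis inclusion criterion 9 requires male subjects and their partners of child-bearing potential to use two birth-control methods, one of them a barrier, and to "make no donation of sperm from Screening until 3 months after the last dose of study drug".

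For women, inclusion criterion 8 in section 4.1 reads: "Women of child-bearing potential must use a highly effective contraception method from Screening through the Follow-Up Visit". Section 3 gives "Follow-Up Period: 10-14 days". Section 7.5 makes pregnancies in female subjects reportable during the study and for 4 weeks after the last dose.

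Section 7.5 also refers to material that is not public: "Please see the Pregnancy Reporting Form Completion Guidelines for safety reporting instructions". For subjects who leave early, section 7.4 states: "Should any subject choose to withdraw from the study, they will be advised of the safety precautions to be taken".

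**The concern.** The male precaution and the partner-pregnancy report appear to guard against the same thing, exposure of a foetus through the father, yet the report covers a much shorter time. A conception in the second or third month after dosing falls where the sponsor still asks men to take care, but where the visible text asks nobody to report it. Adverse-event monitoring under section 7.4 stops at the follow-up visit, so it does not fill the space.

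For women the order is the other way round: reporting outlasts contraception. The visible text does not explain why men have the longer precaution but the same reporting window.

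At stake is the capture of a rare safety event. A site that followed section 7.5 exactly would have no duty to send in such a case or follow it to outcome.

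**Working it through.** The documents give no figure for this gap, so there is none to reproduce. The check is date arithmetic.

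**Inputs**
- Partner reporting scope, section 7.5: 4 weeks = 28 days after the last dose.
- Male precaution, synopsis criterion 9: 3 months after the last dose = 89 to 92 days, depending on the calendar date.
- Follow-up visit, section 3: 10–14 days after the last dose.
- Washout, section 3: 10–14 days. Each treatment period lasts 16 days.
- Sites are blinded (section 5.2.4), so they can count only from the last dose of study medication, active or placebo.

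**Gap from the last blinded dose**
- Shortest: 89 − 28 = 61 days, and 61/89 = 68.5% of the period.
- Longest: 92 − 28 = 64 days, and 64/92 = 69.6%.
- Other readings of 3 months: 12 weeks gives 84 − 28 = 56 days, 90 days gives 62, and 13 weeks gives 91 − 28 = 63.
- With the last dose on Day 46, reporting scope ends at Day 46 + 28 = 74. The precaution ends at Day 46 + 89 = 135 to Day 46 + 92 = 138.

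**By sequence, measured from the last active dose**
- Active second: the last blinded dose is the last active dose, so the gap is the full 61–64 days.
- Active first: the last placebo dose falls 10 + 16 = 26 to 14 + 16 = 30 days after the last active dose. The current window therefore reaches 26 + 28 = 54 to 30 + 28 = 58 days after it. Against 3 months counted from the last active dose, the shortfall is 89 − 58 = 31 to 92 − 54 = 38 days.

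**Women, for comparison**
- Reporting outlasts contraception by 28 − 14 = 14 to 28 − 10 = 18 days.

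**Expected cases (assumptions, not trial figures)**
- Men: section 1 says about 66–75% of chronic-cough patients are women. Applied to 68 subjects, this gives 68 × 0.25 = 17 to 68 × 0.34 = 23 men.
- Assumed share with a partner of child-bearing potential: 10–50%.
- Assumed pregnancy rate: 1–5% per year with two methods, 20% per year with none.
- Low: 17 × 0.10 × 0.01 × 61/365 = 0.003.
- High with two methods: 23 × 0.50 × 0.05 × 64/365 = 0.10.
- High with no contraception in the gap: 23 × 0.50 × 0.20 × 64/365 = 0.40.

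**The case against.** **Different duties.** A reader might infer that the two sections contradict each other. They do not: one sets a precaution, the other says which pregnancies are reported, and nothing in the protocol says the periods must match. The women's periods do not match either. This stands, and it makes the point one of alignment.

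**The 3 months may attach only to sperm donation.** A pregnancy from donated sperm would not be one in a subject's partner, so the comparison would weaken. Yet on that reading male contraception has no end date at all, which makes the wider reading the natural one. The ambiguity remains: the list in section 4.1 stops at criterion 8 in the available text, probably through extraction, so criterion 9 can be read only in the synopsis.

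**The duty does not expire at 4 weeks.** The 4 weeks decide which pregnancies count, while the 24-hour clock starts when the site learns of one. A pregnancy that occurs within the window but is discovered later remains reportable. This is correct, so the gap is one of scope. The *right after* wording could be read more generously, but it sets no limit.

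**Unseen material.** The form guidelines, the Safety Plan and the participant information are not public, and nonclinical data are absent from the available text. Any of these may set or justify another window. A reader might also infer from the visit lists in 6.6.15 and 6.6.16 that men are never told to report a later pregnancy. The documents do not support that: both lists contain blank bullets whose content is unknown.

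**New asymmetry.** Women, who are exposed directly, would keep 4 weeks while partners get 3 months. That is a fair remark, but the longer male period is already the sponsor's own choice in criterion 9.

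**Conclusion.** The point holds as a minor misalignment in safety reporting. Conceptions in about the last 61–64 days of the male precaution, roughly 69–70% of the 3 months after the last blinded dose, are outside the visible scope of section 7.5, although its own rationale would reach them. The full gap applies to men who take active drug second. For men who take it first, part of the period after active exposure is already covered, so it would be wrong to read 61–64 days as lost exposure time for every man.

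The conclusion rests on reading criterion 9 as covering contraception as well as sperm donation, and on the non-public documents not already setting a longer window. Expected cases are about 0.003–0.10 in the whole trial, or up to about 0.4 if every assumed input is at its maximum and no contraception is used. In practice none is likely. Efficacy, the analysis and the sample size are unaffected. Confidence that this is an actual gap in the trial's procedures is low, because the deciding documents cannot be seen.

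**What to change.** 1. Reword the opening of the partner paragraph in section 7.5, for example: *Any pregnancy in the female partner of a male subject that occurs while he is in the study, or up to 3 months after his last dose of study medication (BLU-5937 or placebo), is to be notified to the sponsor no later than 24 hours after the site learns of it.* This also removes the undefined tail.
2. At the last visit, or at early termination, ask male subjects to tell the site of such a pregnancy, if they are not already told.
3. Check the Safety Plan, the form guidelines and the participant information, and change them only if they state a shorter period.

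The women's window and criterion 9 can stay as they are.

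**Cost.** A sentence in section 7.5 and a short instruction to men, with no added visit. Sites would take calls for 89 − 14 = 75 to 92 − 10 = 82 days after the follow-up visit. Because partner pregnancies are classed as SAEs, a rare report may arrive after database lock. It would go to the safety database only. Since blinded sites must count from the last blinded dose, men who took active drug first would be covered to 26 + 89 = 115 to 30 + 92 = 122 days after their last active dose, so an occasional report will be remote from exposure.

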7.6. Serious Adverse Event Reporting

[figure not shown]
The site will notify any SAE to the sponsor, pharmacovigilance, Medical Monitor, Regulatory team and Illingworth, within 24 hours after becoming aware of its occurrence (as per Diamond PV Safety Plan).

If, during follow-up, any non-serious AE worsens and eventually meets the criteria for an SAE, that AE should be recorded as a new SAE.

The initial SAE report must be as complete as possible, including details of the current illness and SAE, and an assessment of the causal relationship between the event and the investigational product(s). Information not available at the time of the initial report (e.g. an end date for the AE, laboratory values received after the report, or hospital discharge summary) must be documented. All follow-up information must be reported as soon as the relevant info is available.

Sponsor Project № CL-5937-02

The notification should be directed to:

The expectedness of an SAE shall be determined by the Sponsor according to the most recent version of the investigator's brochure. An SAE will be considered "unexpected" if the AE is not listed in the investigator brochure or is not listed at the specificity or severity that has been observed; or, if an investigator brochure is not required or available, is not consistent with the risk information described in the general investigational plan or elsewhere in the current application. "Unexpected," as used in this definition, also refers to AEs that are mentioned in the investigator brochure as occurring with a class of drugs or as anticipated from the pharmacological properties of the drug but are not specifically mentioned as occurring with the particular drug under investigation.

Please see the SAE Form Completion Guidelines for safety reporting instructions as per Safety Plan.

